5.5.5 Permitted dose adjustments and interruptions of study treatment

Study treatment dose adjustments are not permitted during the study. Interruptions are permitted if clinically indicated.

Conditions/events that may lead to the study drug interruptions based on Investigator judgment and overall clinical assessment include:

- reported serious adverse event;
- emergency medical condition, unplanned hospitalization, involving use of excluded concomitant medications;
- abnormal laboratory value(s) or abnormal test or examination result(s)

Should the patient interrupt the study drug for whatever reason, both sc and oral study medication must be interrupted. Re-start decision should be made on a case-by-case basis (refer also to [Section 5.5.4](#)). Should the Investigator decide, after informing the Sponsor, to re-initiate treatment with study drug, depending on the duration of the interruption, the first sc and oral dose at re-start may need to take place at the study site to ensure observation in a similar manner as on Day 1.

The reason for the interruption of treatment and date of interruption should be appropriately documented in the source documents as well as in the Dosage Administration Record eCRF.

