5.6.2 Discontinuation of Study Treatment

Discontinuation of study treatment for a patient occurs when study drug is stopped earlier than the protocol planned duration, and can be initiated by either the patient or the Investigator.

The Investigator must discontinue study treatment for a given patient if, on balance, he/she believes that continuation would negatively impact the risk/benefit of trial participation.

Discontinuation of study treatment does not mean discontinuation from study. After stopping the treatment, the patient is encouraged to return for all regular visits as detailed in the schedule of assessments ([Table 6-1](#)). The patient should return to the clinic as soon as possible, after discontinuation of study drug, for an end of treatment visit (EOT). EOT visit assessments should be completed and results recorded in the CRF. The Investigator must determine the primary reason for the patient's premature discontinuation of study treatment and record this information on the appropriate CRF.

Study treatment must be permanently discontinued under the following circumstances:

- Patient wish (withdrawal of consent [Section 5.6.3](#))
- Pregnancy (see [Section 6.5.6](#) and [Section 7.6](#))
- Use of prohibited treatment ([Table 5-1](#))
- Diagnosis of PML
- Patient with active serious infections or reactivation (e.g. tuberculosis, hepatitis B or C)
- Skin and /or mucosal reactions which raise the suspicion of severe generalized major skin reactions (Stevens-Johnson syndrome, or toxic epidermal necrolysis-Lyell's syndrome)
- Hypersensitivity to the study medication
- Any situation in which study participation might result in a safety risk to the patient

- Protocol violation that results in a significant risk to the patient's safety
- Emergence of certain adverse events, such as malignancy (except successfully treated basal cell carcinoma, *in situ* squamous cell carcinoma and *in situ* carcinoma of cervix of uterus), liver failure or, serious chronic infection (such as HIV)
- Laboratory abnormalities (e.g. liver function tests (LFT)) and abnormal test procedure as defined in [Appendix 1](#)
- Severe hypoproteinemia
- Interstitial lung disease or new onset or worsening of pulmonary symptoms, such as persistent cough and dyspnea, with or without associated fever, suspicious of interstitial lung disease
- Non-compliance with study treatment

Study treatment discontinuation should be considered under the following circumstance:

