15.2 Guidance on monitoring of patients with infections

All infections that develop during the study will be reported as AEs on the respective AE eCRF pages. Treatment and additional evaluations will be performed at discretion of the Investigator.

The Investigator should remind the patient of the risk of infections and instruct them to promptly report any symptoms of infections to the Investigator. The patients must also be reminded to always carry their Patient Information Card (with site contact information and which identifies them as participants in a clinical study with investigational and control agents with potential immunosuppressive effects) and to show this to any local healthcare provider they may consult and ask that the Investigator be contacted.

In the case of suspected or confirmed serious (CTCAE, Grade 3-4) or atypical infection, study drug interruption should be considered. The Investigator should inform the Sponsor Medical Advisor of any such cases.

When evaluating a patient with a suspected infection, the most sensitive tests available should be used (i.e. that directly detect the pathogen, as with PCR).

The Investigator should consider early treatment with specific antimicrobial therapy on the basis of clinical diagnosis or suspicion thereof in consultation with infectious disease experts, as appropriate. The Investigator should inform the Sponsor Medical Advisor of any such cases.

Investigators should consider the added immunosuppressive effects of corticosteroid therapy for treatment of MS attack/relapse and increase vigilance regarding infections during such therapy and in the weeks following administration.

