In oncology patients treated with ofatumumab, cases of fatal hepatitis B virus (HBV) reactivation and fatal infection due to hepatitis B in patients who have not been previously infected have occurred (refer to local ARZERRA[®] prescribing information). The MS patients enrolled in the study who are at potential risk of HBV reactivation (e.g. patients with evidence of prior HBV infection (anti-HBc positive and HBsAg negative) and whose HBV DNA test is negative at Screening, should be closely monitored for signs of active HBV infection or reactivation during the study. In patients with suspicion of HBV infection (active/reactivation), laboratory testing for HBV should be done. For patients who show evidence of hepatitis B infection (HBsAg positive [regardless of antibody status] or HBsAg negative but anti-HBc positive), the Investigator is advised to consult with physicians with expertise in managing hepatitis B regarding monitoring and consideration for HBV antiviral therapy.

In patients who develop reactivation of HBV while receiving study drug, immediately discontinue study drug and institute appropriate treatment and follow up.

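### Section 15.2 and the last row of Table 13-2 make optional some study-drug stops that Section 5.6.2 makes mandatory and permanent

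*Protocol*

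**What the plan says.** Protocol Section 5.6.2 opens its list with "Study treatment must be permanently discontinued under the following circumstances". One bullet reads "Patient with active serious infections or reactivation (e.g. tuberculosis, hepatitis B or C". Another covers certain adverse events: malignancy (apart from treated skin and in situ carcinomas), then "liver failure or, serious chronic infection (such as HIV".

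Protocol Section 15.2, the appendix section a site would consult for an infection, says: "In the case of suspected or confirmed serious (CTCAE, Grade 3-4) or atypical infection, study drug interruption should be considered". It adds: "The Investigator should inform the Sponsor Medical Advisor of any such cases". Its one firm stop is for hepatitis B: "In patients who develop reactivation of HBV while receiving study drug, immediately discontinue study drug".

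For the liver, the last row of Table 13-2 deals with any adverse event that might indicate liver toxicity. It asks the site to consider interrupting or discontinuing study treatment. The asterisk note under Table 13-1 defines these events, and hepatic failure and malignant liver neoplasm are among them. Section 7.3 is equally soft: for liver events, the drug is discontinued if appropriate.

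Neither Section 15.2 nor Appendix 1 refers to Section 5.6.2. The only link runs the other way: Section 5.6.2 points to Appendix 1 for laboratory abnormalities.

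**The concern.** The main body sets a mandatory, permanent stop. The text written for the specific event offers an optional and possibly temporary one, and the protocol does not say which prevails. A site handling confirmed active tuberculosis is likely to open the infection appendix first. If it goes no further, it could interrupt dosing and later restart an immunosuppressive study drug that Section 5.6.2 says must stop for good.

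What is at stake is the safety of individual patients, not the trial's conclusions. SAP Section 2.5.4 includes all data up to the end of the treatment epoch, on or off study drug, so a stop or restart does not remove a patient from the primary analysis.

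**Working it through.** No arithmetic on trial data applies. The check sets the texts side by side.

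| Condition | Section 5.6.2 | Event-specific text | Result |
|---|---|---|---|
| Hepatitis B reactivation | Permanent stop | 15.2: discontinue immediately | Agrees, though permanence is not repeated |
| Active tuberculosis | Permanent stop | 15.2: consider interruption if Grade 3-4 or atypical | Weaker |
| Active hepatitis C | Permanent stop | 15.2: as for tuberculosis | Weaker |
| Serious chronic infection (HIV) | Permanent stop | 15.2: as for tuberculosis | Weaker |
| Liver failure | Permanent stop | Table 13-2, last row: consider | Weaker, but often caught by another row |
| Malignant liver neoplasm | Permanent stop (malignancy) | Table 13-2, last row: consider | Weaker |

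**Extent of the wording gap**

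- Section 5.6.2 has 14 mandatory-stop bullets. Two are affected: the infection bullet and the bullet on certain adverse events.
- Apart from PML, Section 5.6.2 names four infections: tuberculosis, hepatitis B, hepatitis C and HIV. Section 15.2 repeats the stop for one of them, so 4 − 1 = 3 remain.
- Table 13-2 has 11 action rows: 5 require an immediate stop, 2 require a stop if the elevation persists, 3 require no stop, and 1 says consider (5 + 2 + 3 + 1 = 11). The gap lies in that one row.
- The footnote to that row covers 8 conditions: hepatic failure, fibrosis, cirrhosis, other liver damage, non-infectious hepatitis, and benign, malignant and unspecified liver neoplasm. Two of the 8 are permanent stops under Section 5.6.2.

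**Could a restart follow?**

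1. Section 5.5.5 gives a "reported serious adverse event" as a possible ground for interruption and foresees resumption: "Should the Investigator decide, after informing the Sponsor, to re-initiate treatment with study drug". That is a duty to inform, not a requirement for approval.
2. Section 5.5.4 lets a patient resume after an interruption if the investigator judges it safe. It asks for the Medical Advisor to be told before restart only when two or more consecutive monthly injections have been missed.
3. Section 15.2 contains no bar on restart. Elsewhere the protocol writes one where it wants one, for example in Table 5-1 for immunosuppressants and B-cell depleting agents.
4. The word *discontinue* does not settle the matter. Section 15.4 says the drug must be discontinued for confirmed low immunoglobulins, then allows re-initiation once levels are normal.

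A site that followed Sections 15.2, 5.5.4 and 5.5.5 and overlooked Section 5.6.2 could therefore restart.

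**The case against.** The strongest reply is that no text permits what Section 5.6.2 forbids. Section 5.6.2 is a main-body rule. Section 15.2 belongs to an appendix of guidance and covers a wider group, including suspected and atypical infections. It can be read as an interim step at a lower threshold, with Section 5.6.2 taking over once a listed condition is established. Section 5.6.2 also has a general clause for any situation that puts the patient at risk. This stands to a large extent: a permanent stop complies with every text, so a reader who inferred that sites cannot follow the protocol consistently would be going too far. It does not remove the inconsistency. Section 15.2 expressly includes confirmed infection, and nothing states which section governs.

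The liver part is also narrower than it may seem. Hepatic failure will usually meet a firm-stop row such as potential Hy's Law, raised transaminases with INR above 1.5, or jaundice. That leaves mainly malignant liver neoplasm, which is always a serious event (Section 7.2.1) and reportable within 24 hours (Section 7.2.2). Continued dosing is unlikely, but the cell still understates the rule.

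Two safeguards count as well: the Medical Advisor is to be informed under Section 15.2, and the Sponsor before re-initiation under Section 5.5.5. They reduce the chance of a wrongful restart without prohibiting it.

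A reader might also infer that Section 5.6.2 should say how a recoverable acute Grade 3-4 infection is handled. That section does not define *serious* by CTCAE grade, and Section 7.1 keeps grade and seriousness apart. Whether such an infection should end treatment is a clinical choice for the sponsor. A clause permitting interruption could loosen a stop that now applies, so it is not part of this point.

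**Conclusion.** The point holds as a modest safety-conduct inconsistency. Section 15.2 and the last row of Table 13-2 understate the action that Section 5.6.2 requires, and neither directs the site there. The practical gap is mainly tuberculosis, hepatitis C, HIV and malignant liver neoplasm.

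The number of patients cannot be derived: the documents give no rate for these events. Section 4.2 excludes patients with HIV or at risk of tuberculosis or hepatitis, so few cases are to be expected. The wording counts above describe text, not risk. A reader might infer that patients will be wrongly restarted, or that the efficacy result is exposed. The documents support neither. They show only that a restart is not barred in the places a site is likely to look, and SAP Section 2.5.4 keeps off-treatment data in the primary analysis.

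The conclusion assumes that Section 5.6.2 states the sponsor's intended rule and that some sites will consult the event-specific text on its own.

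**What to change.** Two edits at the next amendment.

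1. Section 15.2, in place of the present sentence on serious or atypical infection: *If the infection meets a permanent-discontinuation criterion in Section 5.6.2 (active serious infection or reactivation, e.g. tuberculosis, hepatitis B or C; or serious chronic infection such as HIV), study drug must be permanently discontinued. For other suspected or confirmed Grade 3-4 or atypical infections, interruption should be considered.* HIV must be named, because it sits in a different Section 5.6.2 bullet and would otherwise fall into the second sentence.
2. Table 13-2, last row, first action: *Hepatic failure or malignant liver neoplasm: permanently discontinue per Section 5.6.2. Other events: consider interruption or discontinuation.*

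Section 5.6.2 itself stays unchanged.

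The cost is one sentence and one table cell. The few patients affected need an end-of-treatment visit if they stay in the Treatment epoch, and at least 9 months of off-drug follow-up (Section 3.1). Section 5.6.2 already implies both.

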5.6.3 Withdrawal of informed consent

Subjects may voluntarily withdraw consent to participate in the study for any reason at any time. Withdrawal of consent occurs only when a subject:

- Does not want to participate in the study anymore, and
- Does not allow further collection of personal data

In this situation, the Investigator should make a reasonable effort (e.g. telephone, e-mail, letter) to understand the primary reason for the subject's decision to withdraw his/her consent and record this information.

Study treatment must be discontinued and no further assessments conducted, and the data that would have been collected at subsequent visits will be considered missing.

Further attempts to contact the subject are not allowed unless safety findings require communicating or follow-up.

All efforts should be made to complete the assessments prior to study withdrawal. A final evaluation (EOS) at the time of the subject's study withdrawal should be made as detailed in the schedule of assessments ([Table 6-1](#)).

Novartis/Sponsor will continue to keep and use collected study information (including any data resulting from the analysis of a subject's samples until their time of withdrawal) according to applicable law.

For US: All biological samples not yet analyzed at the time of withdrawal may still be used for further testing/analysis in accordance with the terms of this protocol and of the informed consent form.

For EU and RoW: All biological samples not yet analyzed at the time of withdrawal will no longer be used, unless permitted by applicable law. They will be stored according to applicable legal requirements.

5.6.4 Loss to follow-up

For patients whose status is unclear because they fail to appear for study visits without stating an intention to discontinue or withdraw, the Investigator should show "due diligence" by documenting in the source documents steps taken to contact the subject, e.g. dates of telephone calls, registered letters, etc. A patient cannot be considered as lost to follow-up until the time point of his/her scheduled End of Study visit has passed.

5.6.5 Early study termination by the Sponsor

The study can be terminated by the Sponsor at any time for any reason. This may include reasons related to the benefit risk assessment of participating in the study, practical reasons, or for regulatory or medical reasons (including slow enrolment). Should this be necessary, the patient must be seen as soon as possible and treated as a prematurely withdrawn patient. The Investigator may be informed of additional procedures to be followed in order to ensure that adequate consideration is given to the protection of the patient's interests. The Investigator will be responsible for informing the Institutional Review Board/Independent Ethics Committee (IRBs/IECs) of the early termination of the trial.

5.6.6 Role of Key site personnel

Key site personnel include (but are not limited to) the following individuals:

Investigator

The Investigator will be responsible for:

- Overall conduct of the study at the study site including assigning per protocol required study staff
 - Management of the routine clinical care of the study patients
 - Administration and supervision of initial sc injections and training/supervision of ability to self/home-administer. The Investigator may delegate this responsibility to the Study Nurse/Study Coordinator as appropriate and permissible by local regulation
 - Confirmation of patient's eligibility for randomization
- 

- Administration of T25FW, 9HPT and SDMT (may be delegated to the Independent EDSS rater, a back-up physician, a Study Nurse/Study Coordinator or other accordingly experienced medical professionals)
- Referral of patients with neurological symptoms consistent with MS relapse to the Independent EDSS Rater
- Management of adverse events and MS relapses
- Review of patient diaries
- Ensuring that all site personnel are informed of concomitant medications excluded per protocol (e.g. the use of systemic steroids other than for the treatment of MS relapses or as pre-medication before injection)

It is strongly recommended that the Investigator remain unchanged throughout the entire course of the study. Occasionally, the Investigator may designate other medical personnel/health care professionals (other than the Independent EDSS Rater, e.g., a back-up physician or Study Nurse/Study Coordinator) at the study site to perform some of the tests and evaluations listed above. The Investigator is also responsible for ensuring access to appropriate expertise for consultation (e.g. infectious disease, ECG interpretation, mental health care) during the study as needed.

Independent EDSS Rater

The Independent EDSS Rater will be responsible for:

- Obtaining an EDSS score based on detailed neurological examination of patients with neurological symptoms consistent with MS relapse as referred by the Investigator at scheduled or unscheduled visits
- Obtaining an EDSS score based on detailed neurological examination at scheduled visits
- Administration of T25FW, 9HPT and SDMT if delegated by the Investigator and if experienced with the administration of these assessments

The Independent EDSS Rater is a physician, or other trained healthcare professional who is qualified to perform the neurological examination and has been trained and certified as an EDSS rater.

The Independent EDSS Rater must not be involved in any other aspect of the patient's care and/or management of his/her MS treatment and have no access to patient study data.

To ensure consistency in the EDSS scoring across Raters, the Independent EDSS Rater must participate in the standardized training and certification session on EDSS scoring (unless already certified at required level (highest level) in past 12 months) prior to enrollment of patients at their site and will need to obtain recertification on a yearly basis. The Independent EDSS Rater should remain the same throughout the study, whenever possible.

The communication of new neurological findings on the neurological examination, including the EDSS score, from the Independent EDSS Rater to the Investigator is not permitted after Randomization. The roles of the Investigator and the Independent EDSS Rater, including their back-ups, are not interchangeable. The Independent EDSS Rater must remain blinded to

adverse events, concomitant medications, laboratory data and any other data that have the potential of revealing the treatment assignment.

The patient and his/her caregiver should be instructed to take care not to discuss aspects of the patient's treatment or potential AEs, including injection site reactions, with the Independent EDSS Rater. During the examination, the patient should wear appropriate clothing that covers injection sites.

Study Nurse/Study Coordinator

The Study Nurse/Study Coordinator's responsibilities may include:

- Assisting the Investigator in patient management, including the assessment and treatment of adverse events, MS relapses and the recording of adverse events, concomitant medications and monitoring of compliance (returned capsule and syringe counts)
- Administration and supervision of initial injections and training/supervision of ability to self/home-administer as delegated by the Investigator
- Administration of T25FW, 9HPT and SDMT as delegated by the Investigator and if experienced with the administration of these assessments
- Scheduling visits and assessments as outlined in the protocol, maintaining proper source documentation and transcription of the data to the CRFs
- Coordination with and between the study selected central labs, drawing and processing lab samples
- Ensuring patient understanding of injection handling and home administration instructions, questionnaires, diaries and the completion of these
- Providing patient with a Patient Information Card (identifying patients as study participant in a clinical trial with pertinent information and site contact information (see also [Section 15.2](#))
- Conducting monthly phone calls with the study patients, as delegated by the Investigator

MRI technician

The MRI technician will be responsible for:

- Familiarization with the MRI manual procedures and the study specific MRI protocol
- Performance of a "dry" or "dummy" run using the MRI parameters outlined by the MRI protocol
- Performance of high-quality MRI scans using the study specific parameters stored in the designated MRI scanner for the duration of the study
- Submission of the MRIs in the appropriate format to the central MRI reader immediately upon completion

Neuroradiologist/Radiologist

The local neuroradiologist/radiologist will be responsible for:

- Reviewing each MRI scan performed for the study patients and contacting the Investigator in case of unexpected safety-related findings detected on the MRI scan

6 Visit schedule and assessments

Table 6-1 lists all of the assessments and indicates with an “x” when the visits are performed.

Patients should be seen for all visits on the designated day per the schedule of assessments, or as close to it as possible within the visit windows. Missed or rescheduled visits should not lead to automatic discontinuation.

In case a visit is performed outside the schedule, subsequent visits shall be performed in keeping with the original visit schedule (one month is defined as 28 calendar days). In addition to the scheduled visits, patients may have unscheduled visits due to a MS relapse, an acute illness of undetermined cause, for other reasons, or at the discretion of the Investigator. Data collected during unscheduled visits will be recorded in the unscheduled visit CRFs.

Patients who stop taking study medication should be scheduled for the end of treatment (EOT) visit as soon as possible. The patients will be asked to remain in the study and continue completing the study visits and assessments (shaded in Table 6-1) until the end of the study (EOS).

End of treatment (EOT) visit is not mandatory for all patients. It is only applicable to patients who prematurely discontinue double-blind study treatment and will continue to follow the assessment schedule of the Treatment epoch (Table 6-1).

End of study (EOS) visit is mandatory for all patients. The EOS Visit is conducted at the end of the Treatment epoch (i.e. when the patient has completed up to 30 months, or when EOS is declared for all patients, or at time of premature withdrawal from study). At the time EOS is declared for all patients, all patients ongoing in the Treatment epoch should be contacted and their EOS Visit should be scheduled to occur as soon as possible.

Patients who prematurely discontinued study drug but do not agree to continue to be followed in the study Treatment epoch per Table 6-1, but agree to continued safety follow up, will have their EOS Visit and then enter the Safety Follow-up (FU) according to schedule in Table 6-2 .

Patients who complete the Treatment epoch on study drug but do not enter the Extension study, will have their EOS Visit and then enter the Safety Follow-up (FU) schedule in Table 6-2.

During the study, patients will be asked to complete a diary from Month 1 onwards to record information pertinent to study drug administration (including date and time of sc injections) and home pregnancy testing (date and results) for females of childbearing potential. The patient is requested to bring the completed diaries with them to each visit and the Investigator/Study Nurse/Study Coordinator must review these for completeness and for potential AEs, injection related reactions, study drug interruptions etc. and record information obtained from the diaries on the relevant CRFs.

A structured telephone interview script provided for the study will be conducted by site personnel every month starting at Month 2 (Table 6-1). The interview should take place around time of the monthly sc self/home-injection to query about any new or worsening symptoms

warranting an unscheduled visit, injection reactions, and, as applicable, results of home pregnancy testing, compliance with contraception requirements and with any scheduled local LFT lab testing.

Some protocol procedures may be done via an outpatient setting (e.g. at patient's home) with the support of study staff or a healthcare professional registered with the study site for the study, if this is permissible per the local regulatory authority.

Table 6-1 Assessment schedule

Epoch	Screening		Treatment											
Visit	SCR (D-45 to D-8)	BL (D -7 to D1 (pre- treat ment)	D1 ¹	D7	D14	M1	M3	M6	M9	M12/24	M15/21/27 ⁹	M18	EOT ⁹	EOS ⁹
Visit No.	1	2	101	102	103	104	105	106	107	108/112	109/111/113	110	198	199
Visit Window (days)	n.a.	n.a.	n.a.	±1	±1	±3	±14	±14	±14	±14	±14	±14	n.a.	n.a.
Informed consent	X													
Demography, Height	X													
Medical history	X													
MS History/Treatments	X													
Incl/Excl	X ¹⁸	X												
IRT contact	X		X	X	X	X	X	X	X	X	X	X	X	X
Dispense study drug			X	X	X	X	X	X	X	X	X	X		
Phone interview						monthly between scheduled visits ¹¹								
Physical Exam ²¹	X ^{2a}	X ^{2a}						X		X		X	X	X
Patient diary review							X	X	X	X	X	X	X	X
Contraception status ¹⁶	X	X				X	X	X	X	X	X	X	X	X
Vital signs, Weight	X	X	X ²⁰	X ²⁰	X ²⁰	X ²⁰	X	X	X	X	X	X	X	X
Routine lab samples ¹⁹ , including urine	X ³	X ²³				X	X	X	X	X	X	X	X	X
Sample for B-cells	X	X		X	X	X	X	X	X	X	X	X	X	X
Teriflunomide plasma levels														X ¹⁵
Additional LFT testing					X ¹⁰	X ¹⁰								
Sample for Total IgG, IgM	X ^{2a}	X ^{2a}				X	X	X	X	X	X	X	X	X

Epoch	Screening		Treatment												
Visit	SCR (D-45 to D-8)	BL (D -7 to D1 (pre- treat ment))	D1 ¹	D7	D14	M1	M3	M6	M9	M12/24	M15/21/27 ⁹	M18	EOT ⁹	EOS ⁹	
Visit No.	1	2	101	102	103	104	105	106	107	108/112	109/111/113	110	198	199	
Pregnancy Test ⁴	X		X			X	X	X	X	X	X	X	X	X	
ECG	X ^{2a}	X ^{2a}											X	X	
MRI	X									X			X ⁸	X ⁸	
AEs	X	X	X	X	X	X	X	X	X	X	X	X	X	X	
Prior/Con Meds ¹⁴	X	X	X	X	X	X	X	X	X	X	X	X	X	X	
Sample for population PK ¹³		X				X	X	X		X			X	X	
Sample for ADA ¹³		X				X		X		X			X	X	
Samples for biomarkers ²²	X ^{2a}	X ^{2a}					X			X			X	X	
eCSSRS	X ⁶	X ⁶	X	X	X	X	X	X	X	X	X	X	X	X	
MS Relapse			X	X	X	X	X	X	X	X	X	X	X	X	
EDSS	X	X ^{2b}	X ^{2b}				X	X	X	X	X	X	X	X	
T25FW	X ^{2a}	X ^{2a}					X	X	X	X	X	X	X	X	
9HPT	X ^{2a}	X ^{2a}						X		X		X	X	X	
SDMT (oral)	X ^{2a}	X ^{2a}						X		X		X	X	X	
MSIS-29 ⁷	X ^{2a}	X ^{2a}						X		X		X	X	X	
PRO completion form	X ^{2a}	X ^{2a}						X		X		X	X	X	
AEP			X ¹²												
End of Treatment														X	X ¹⁷

Epoch	Screening		Treatment											
Visit	SCR (D-45 to D-8)	BL (D -7 to D1 (pre- treat ment))	D1 ¹	D7	D14	M1	M3	M6	M9	M12/24	M15/21/27 ⁹	M18	EOT ⁹	EOS ⁹
Visit No.	1	2	101	102	103	104	105	106	107	108/112	109/111/113	110	198	199
Study Phase Completion														X

ADA= Anti-drug-antibody ; AEs= Averse events; AEP= Accelerated elimination procedure; BL=baseline; D= day; ██████████ eCSSRS=electronic Columbia-Suicide Severity Rating Scale; EDSS=Expanded Disability Status scale; ██████████ ; EOS=End of Study; EOT=End of Treatment; Excl.=exclusion; HPT=9-Hole Peg Test; Ig= immunoglobulin; Incl.=inclusion; IRI= Interactive response technology; LFT=liver function test; M=month; MRI=magnetic resonance imaging ;MS=multiple sclerosis; MSIS= Multiple Sclerosis Impact Scale; n.a=not applicable; PK=pharmacokinetic; PRO= Patient Reported Outcome; SDMT= Symbol Digit Modalities Test; T25FW=Timed 25-foot Walk; ██████████

1. Randomization and first dose (usually expected on the same day). If first dose occurs on a different day after randomization, the day of first dose should be considered to be Day 1
 2. a) Assessment can be conducted either at Screening OR Baseline visit b) Assessment can be conducted at either the Baseline OR the Day 1 visit (they must be conducted before the first dose of investigational treatment).
 3. Serology testing to check patient eligibility conducted at Screening only
 4. Female patients only: Serum pregnancy tests will be conducted at Screening, EOT and EOS Visits. Urine pregnancy test on Day 1 should be conducted prior to dosing on Day 1. Urine pregnancy tests will be conducted at all other scheduled visits as indicated in Table 6-1. In addition monthly urine pregnancy tests will be conducted between clinic visits. The patient must contact the Investigator immediately in the case of a positive test for confirmatory testing at the Investigator’s discretion
- ██████████
██████████
6. The eCSSRS must be assessed once before randomization, either at the Screening (recommended) or the Baseline visit.
██████████
██████████
 8. MRI scan at the End of Treatment (EOT) and/or End of Study (EOS) is needed if there was no MRI scan in the last 3 months
 9. For patients who reach Month 27 visit, the next (and last) 3-monthly scheduled visit is the EOS Visit; EOS assessments will be done for all patients; End of treatment (EOT) assessments are done only for patients who prematurely discontinue study drug (at the time of study drug discontinuation) and who continue to stay in the Treatment epoch
- ██████████

10. Additional monthly LFT testing will be required at Month 2, 4 and 5 i.e. between scheduled lab visits in first 6 months in all patients. More frequent LFT testing may be required in patients in countries/regions where the local teriflunomide prescribing information stipulates more frequent LFT testing. E.g. in the EU LFT testing should be performed every 2 weeks in the first 6 months and every 8 weeks thereafter (i.e., once between 3-monthly scheduled visits). A local lab for the additional LFT testing may be used ([Section 6.5.4.2](#))
 11. Telephone interview by site staff every month starting at Month 2. The interview should take place around time of the monthly sc self/home injection to query about any new or worsening symptoms warranting an unscheduled visit, injection reactions, results of home pregnancy testing, compliance with contraception requirements and compliance with local LFT lab testing as applicable
 12. AEP: applicable only for patients who have permanently discontinued study drug. Patients may undergo an accelerated elimination process at Investigator's discretion ([Section 7.8](#))
 13. PK and ADA visits: at the Month 1 visit, the PK and ADA samples should be drawn before the patient takes their Month 1 injection. For later PK and ADA visits, if the monthly injection is scheduled for the same day as the visit, the patient should take the injection after the PK/ADA sample has been drawn (patient should be instructed not to take the injection before coming to the site for the visit)
 14. Including corticosteroids used to treat MS relapse; any newly started MS treatment as applicable (for patients who have discontinued study medications)
 15. Only for patients who had EOT \geq 9 months earlier
 16. Patients contraception status must be reviewed and documented to ensure method of contraception continues to be appropriate per protocol requirement for highly effective contraception
 17. Only for patients for whom the EOT page has not already been completed (i.e. have not had an EOT visit)
 18. Syphilis and Tuberculosis testing must be done as part of eligibility check (Exclusion criterion #11) unless completed in the last 6 months prior to screening with documented negative results. If sites don't have the possibility to test tuberculosis locally, Quantiferon®-TB Gold test may be requested to be done by the Central laboratory to assess patient's eligibility.
 19. More frequent hematology testing (excluding B-cells and IgG and IgM for blinding purpose) may be performed by local laboratory if this is required by the local regulatory authority
 20. Vital signs should be obtained 30-60 min before sc injection (if premedication is administered, pre-injection vital signs should be obtained before premedication is administered), and again approximately 60 min post-injection on Day 1, Day 7, Day 14 and Month 1
 21. A complete physical examination will be performed at the visits indicated in [Table 6-1](#) and will include an assessment of skin, head and neck, lymph nodes, heart, lungs, abdomen, back, neurological function and comments on general appearance. A complete neurological examination will be part of the initial physical examination at Screening
 22. Samples for biomarkers will be collected as described in [Section 6.6.5](#)
 23. Labs must be drawn to allow adequate time for results to be obtained before randomization to ensure patient's eligibility
- Note: Patients who have prematurely discontinued study drug (EOT) and continue to be followed under the [Table 6-1](#) schedule after study drug discontinuation, will only do the assessment shaded in grey

Table 6-2 Assessment schedule for Safety Follow-up epoch

Visit Month ¹ (relative to EOS)	+M3	+M6	+M9	Every 3 months ⁵	End of Safety-FU ²
Visit Number	201	202	203	204/20X	299
Visit window (days)	±14	±14	±14	±14	
AEs	X	X	X	X	X
Concomitant Meds*	X	X	X	X	X
Vital Signs	X	X	X	X	X
eCSSRS	X	X	X	X	X
Urine pregnancy test ³	X	X	X	X	X
Contraception status	X	X	X	X	X
Routine lab samples	X	X	X	X	X
Sample for Total IgG, IgM	X	X	X	X	X
Sample for B-cells	X	X	X	X	X
Sample for teriflunomide plasma level ⁶	X	X	X	X	X
MS Relapse	X	X	X	X	X
EDSS	X	X	X	X	X
AEP	X ⁴				

AEs= Averse events; AEP=Accelerated elimination procedure; DMT=disease modifying therapy; eCSSRS=electronic Columbia-Suicide Severity Rating Scale; EOS=End of Study; FU=Follow-up

1. Time measured from the EOS Visit. M=month.
 2. If scheduled visit and End of Safety-FU occur at the same time only End of Safety-FU visit should be done. If patient is prematurely withdrawn from the Safety-FU epoch, the End of Safety-FU assessments should be done at time of withdrawal.
 3. Female patients only: monthly urine home pregnancy testing will be conducted between clinic visits. The patient must contact the Investigator immediately in the case of a positive test for confirmatory testing at the Investigator's discretion.
 4. AEP. Patients may undergo an accelerated elimination process at Investigator's discretion as described in [Section 7.8](#)
 5. As needed for patients requiring prolonged B-cell/teriflunomide plasma level monitoring ([Section 3.1](#))
 6. As needed (teriflunomide level assessed only when patient has had a total of at least 9 months of follow up and then 3-monthly as needed after study drug discontinuation as described in [Section 3.1](#))
- *including steroids for MS relapse and newly started DMT as applicable

